SECONDARY OBJECTIVE:	
WP 1: SEROLOGY MANDATORY
 
Evaluate the humoral response to a Covid-19 infection in the following subgroups:
 
 In patients with cancer who are symptomatic with a probable Covid-19 infection In patients whose treatment has been suspended In patients with treatment currently ongoing: 
 Patients receiving immunotherapy Patients receiving chemotherapy: 
 Patients with neutropenia-inducing chemotherapy Patients with lymphopenia-inducing chemotherapy In healthcare personnel of the CLCCs 
Describe the diagnostic performance of serological tests (IgM rapid test and IgM serological test).
 
Describe long-term IgG persistence and quantification (Month 12) in populations from the CLCCs.
 
Among individuals who developed IgG:
 
 describe the frequency of reinfections in each study population. describe the protective IgG threshold in each study population. 
Evaluate the influence of polymorphisms in low-affinity Fc gamma receptors for IgG (FcγRIIa, FcγRIIIa) on the humoral response.
 
Evaluate the appearance of IgG and their evolution during study follow-up after vaccination.
 
Evaluate the number of individuals presenting antibodies after vaccination.

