	
Evaluate the neutralizing capacity of IgG (neutralization assays) after vaccination over the duration of the study.
 
WP 2: CLINICAL MANDATORY
 
Describe severity (asymptomatic, symptomatic, prolonged, severe, fatal) by age group:
 
 In healthcare personnel In cancer patients In patients in follow-up In patients undergoing treatment: 
 Receiving chemotherapy and according to whether the chemotherapy induces grade 3–4 neutropenia or lymphopenia (as defined in the primary literature) Receiving immunotherapy 
Determine the frequency of Covid-19 reinfection (recurrence of clinically suggestive symptoms with positive viral PCR and/or positive IgM serology) during follow-up in the different groups.
 
Identify risk factors (clinical and therapeutic) for developing severe forms of Covid-19 infection among patients.
 
WP 3: ECONOMIC ANALYSIS OPTIONAL FOR CENTERS
 
Describe the consequences of Covid-19 in terms of organizational changes and care practices, from the start of the epidemic until the end of systematic screening for patients and healthcare personnel.
 
Identify changes in healthcare personnel practices regarding:
 
Coordination between healthcare workers
 
 Communication Patient management 
Identify resources associated with organizational changes at the level of:
 
 Modification of treatment regimens for patients (e.g., chemotherapy, radiotherapy, surgery) Organization of teleconsultations Diagnostic investigations for new cancers 
Analyze the impact of changes on patient health status.
 
Evaluate resources allocated to:
 
 The organizational changes described above Systematic screening of patients and healthcare personnel Work stoppages. 
WP 4: PUBLIC HEALTH / EPIDEMIOLOGY OPTIONAL FOR CENTERS
 
Identify risk factors for SARS-CoV-2 infection among patients, including:
 
 Sociodemographic factors (age, socio-professional category, housing, cohabitation) Lifestyle (work modalities, mobility, protective measures, etc.) Contact with infected individuals at work or at home Care pathway in CLCCs (number and duration of visits, number of care units visited, etc.), use of community care 
Estimate SARS-CoV-2 infection prevalence at the end of the lockdown:
 
 among patients among healthcare personnel who continued onsite work among healthcare personnel who were confined 
Identify risk factors for Covid-19 infection among healthcare personnel, including:
 
 Sociodemographic factors (age, socio-professional category, housing, cohabitation) Lifestyle (work modalities, mobility, protective measures, etc.)

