--	---

	
c. Contact with infected individuals at work or at home d. Use of community care
 
Describe the incidence of Covid-19 infections among patients and healthcare personnel.
 
Compare the distribution of contamination risk factors among patients and those of the general population (Constances cohort).
 
Describe adherence to SARS-CoV-2 vaccination among personnel and patients.
 
WP 5 : PSYCHOLOGY OPTIONAL FOR CENTERS
 
Examine the evolution of state anxiety over time and determine whether perceptions of anxiety evolve, indicating a possible adaptation process.
 
Examine associations between post-traumatic growth, trait anxiety, sociodemographic variables, and the evolution of state anxiety over time.
 
Examine the evolution of depression over time and determine whether perceptions of depression evolve, indicating a possible adaptation process.
 
Examine associations between post-traumatic growth, trait anxiety, sociodemographic variables, and the evolution of depression over time.

INCLUSION CRITERIA:	
 1) Age \geq 18 years; 2) Population from a CLCC meeting one of the following three definitions: 
  patients undergoing treatment,  patients in follow-up (having completed their treatment more than one year prior to inclusion),  healthcare personnel; 3) Subjects having had or not had an infection compatible with, or confirmed as, Covid-19; 4) Subjects informed and having signed the informed consent form; 5) Subject affiliated with a social security system.
NON-INCLUSION CRITERIA:	
 1) Refusal to provide consent; 2) Patients unable to give consent or presenting psychiatric history; 3) Inability to comply with medical follow-up for geographical, social, or psychological reasons; 4) Individuals under legal protection (guardianship or curatorship); 5) Individuals deprived of liberty by judicial or administrative decision.
PRIMARY EVALUATION CRITERION:	
Biological data: Serological status (rapid immunochromatographic test) and IgM and IgG titers (enzyme immunoassay, ELISA type), performed at M0, M3, M6, M9, and M12. Collection via questionnaire of results from tests detecting SARS-CoV-2 viral genome (RT-PCR molecular test) performed in community settings
 
Clinical data: Follow-up questionnaire on clinical signs suggestive of Covid-19.

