	
Time to appearance and titers of anti-SARS-CoV-2 antibodies according to FCGR2A and FCGR3A genotypes.
 
IgG-positive results on rapid TROD tests and semi-quantitative ELISA IgG titers in vaccinated individuals.
 
Number of vaccinated individuals in whom anti-Spike protein IgG titration is feasible.
 
Number of vaccinated individuals with positive neutralization test results.
 
WP 2: CLINICAL MANDATORY
 
Number of Covid-19-related deaths, severe infections (requiring oxygen therapy), prolonged symptomatic infections, moderate infections, and asymptomatic infections, relative to all subjects in the population with seropositivity and/or a positive RT-PCR test, as well as duration of the symptomatic phase.
 
Reinfection cases are defined as recurrence of clinical symptoms and/or positive viral PCR and/or positive IgM serology after a symptom-free interval. Frequency is defined as the number of reinfection cases relative to all subjects in the population with seropositivity and/or a positive RT-PCR test.
 
Among subjects in the population with seropositivity and/or a positive RT-PCR test, factors significantly associated with severe forms / mortality among the following:
 
 ○ Ongoing or recent anticancer treatment: 
 - Immunotherapy - Chemotherapy, according to frequency of grade 3/4 neutropenia and/or lymphopenia - Radiotherapy - Surgery ○ Concomitant treatments ○ Comorbidities ○ Cancer (cancer type, stage, etc.) ○ Cancer-related medical history (number of treatment lines, surgical and medical history) ○ Biological markers (CRP, etc.) 
WP 3: ECONOMIC ANALYSIS OPTIONAL FOR CENTERS
 
Type of organizational and practice changes implemented and their frequency according to specialties/services.
 
Total number of patients affected and number of patients per type of change.
 
Positive or negative effects on patient morbidity or mortality.
 
Monetary value of resources mobilized (increased or decreased) depending on observed changes.
 
Number and duration of healthcare personnel sick leave.
 
Benefits of organizational changes for healthcare personnel.
 
Costs of systematic screening of patients and healthcare personnel..
 
WP 4 : PUBLIC HEALTH / EPIDEMIOLOGY OPTIONAL FOR CENTERS
 
Number of SARS-CoV-2 infections among all monitored patients.
 
Prevalence of SARS-CoV-2 infection/immunization during the 3 weeks following the end of lockdown among patients, healthcare personnel working onsite, and healthcare personnel who were confined, by age group, by region (center), and according to comorbidities.
 
Number of SARS-CoV-2 infections among all monitored healthcare personnel.
 
Quarterly incidence rates among patients and healthcare personnel by age group, by region (center), and according to comorbidities.
 
Percentages (qualitative variables) / means or medians (quantitative variables).

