--	--

	
Percentage of personnel and patients refusing vaccination, and distribution according to reasons for refusal.
 
WP 5 : PSYCHOLOGY OPTIONAL FOR CENTERS
 
a. and b. State anxiety score at 3, 6, 9, and 12 months. c. and d. Depression score at 3, 6, 9, and 12 months.
 
Variables assessed at T0 (before screening) State anxiety (STAI-State questionnaire, Spielberger, Gorsuch, Lushene, Vagg & Jacobs, 1983; 20 items) Post-traumatic growth (PTGI, Tedeschi & Calhoun, 1996; 21 items; induction instruction: "since the lockdown"). The PTGI evaluates perceived positive changes such as shifting life priorities, closer relationships with others, developing new interests, etc. Trait anxiety (STAI-Trait questionnaire, Spielberger et al., 1983; 20 items) Sociodemographic variables (related to the Epidemiology WP) Depression (HADS questionnaire, Zigmond & Snaith, 1983; 14 items)
 
At 3, 6, 9, and 12 months (within the week following screening) State anxiety (STAI-State, 20 items) Depression (HADS, 14 items)

--	---

E) DESCRIPTION OF THE STUDY INTERVENTIONS

In this study, screening of patients and healthcare personnel will be performed using two or even three techniques depending on the result:

- **Repeated blood sampling, performed at inclusion (M0), Month 3 (M3), Month 6 (M6), Month 9 (M9), Month 12 (M12), plus on demand in the event of Covid-19 symptoms:**
 - a) Rapid serological test (TDR) — qualitative
 - Performed immediately on site.
 - Technique: immunochromatography strip detecting IgM / IgG.
 - b) Serology by ELISA — quantitative
 - Performed later on frozen samples.
 - c) Genotyping of FCGR2A and FCGR3A genes
 - Performed only at M0.
- **Nasopharyngeal swab (RT-PCR)**
 Detection of viral RNA.

This examination is performed with immediate result exclusively in the event of symptoms, irrespective of the rapid test result, for patients hospitalized in a Covid unit when such a unit exists within the center.

Results of RT-PCR tests performed in community settings (outside the hospital) will be collected via questionnaires.

- **Questionnaires** (Linked to the Work Packages — some are therefore optional)
 - Patients : Q1, Q2, Q3
 - Healthcare personnel : Q1, Q2, Q3, Q4, STAI (ETAT & TRAI), PTGI, HADS

TRIAL SCHEDULE

INCLUSION PERIOD:	12 months
DURATION OF PARTICIPATION PER SUBJECT:	12 months
MINIMUM PARTICIPATION TIME PER PATIENT:	12 months
OVERALL STUDY DURATION:	24 months
START OF THE CLINICAL TRIAL:	June 2020

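### The WP2 reinfection frequency divides cases by all ever-positive subjects and ignores that observed time after a first positive runs from about 12 months to none

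*Protocol*

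**What the plan says.** The WP 2 objective (section D, Secondary objective) is: "Determine the frequency of Covid-19 reinfection", to be given "during follow-up in the different groups". The matching WP 2 entry under the completion evaluation criteria defines a case: "Reinfection cases are defined as recurrence of clinical symptoms and/or positive viral PCR and/or positive IgM serology after a symptom-free interval". It then defines the measure: "Frequency is defined as the number of reinfection cases relative to all subjects in the population with seropositivity and/or a positive RT-PCR test". It sets no start of the risk period, no minimum observation after the first infection, no person-time and no handling of death.

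Three other entries determine how long a subject can be watched for a second infection:

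- The trial schedule sets the item "DURATION OF PARTICIPATION PER SUBJECT" at 12 months. The minimum participation time is also 12 months.
- The primary evaluation criterion has serology "performed at M0, M3, M6, M9, and M12". Section E adds samples on demand when there are symptoms.
- Inclusion criterion 3 admits "Subjects having had or not had an infection compatible with, or confirmed as, Covid-19".

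For infection in general, the WP 4 criteria do use a time-based measure, namely incidence rates by quarter.

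**The concern.** Participation runs from inclusion, whereas the risk of reinfection starts only after a first infection. Because first infections can fall before M0 or at any time up to M12, members of the same denominator have very different opportunities to become a case. A subject first positive at M12 cannot be seen to be reinfected and can only dilute the figure. A subject who dies or is lost soon after the first infection has the same effect.

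Two consequences follow. The proportion falls short of the 12-month risk of reinfection, which is how a reader of a 12-month cohort is likely to take it. And when it is tabulated for treated patients, follow-up patients and staff, a difference may reflect when each group met the virus rather than how readily its members are reinfected.

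This is a rule that the protocol states, not a detail left for the SAP. A SAP that reports only this proportion inherits the problem.

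**Working it through.** The protocol gives no reinfection rate, no distribution of first infections over time and no mortality after infection, so there is no figure of its own to reproduce. All hazards, mixes and mortalities below are assumptions. From the protocol come the 12 months of participation and the visits at M0, M3, M6, M9 and M12, which leave 12, 9, 6, 3 or 0 months of observation after a first positive.

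**1. Two timing patterns, same hazard, no deaths.** Let the reinfection hazard be λ = 0.01 per month in everyone.

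- All infected before M0: 1 − exp(−0.01 × 12) = 11.31%.
- First infections spread evenly over follow-up, so that remaining time is uniform on 0 to 12 months: 1 − [1 − exp(−0.12)]/0.12 = 1 − 0.1131/0.12 = 5.77%.
- Ratio: 11.31/5.77 = 1.96.

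**2. Mixed groups.** The mix is the decisive input, so it is varied.

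| Share infected before M0, group A vs group B | Frequency A | Frequency B | False ratio |
|---|---|---|---|
| equal | same | same | 1.00 |
| 70% vs 30% | 0.7 × 11.31 + 0.3 × 5.77 = 9.65% | 0.3 × 11.31 + 0.7 × 5.77 = 7.43% | 1.30 |
| 100% vs 0% | 11.31% | 5.77% | 1.96 |

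Changing the hazard hardly matters. From 0.5% to 2% per month, the extreme ratio goes from 1.98 to 1.92 and the 70/30 ratio from 1.30 to 1.29.

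**3. Using the visit schedule.** Assume a 12-month reinfection risk of 5%. The risk over T months is 1 − 0.95^(T/12): 5.000%, 3.774%, 2.532%, 1.274% and 0% for a first positive at M0, M3, M6, M9 and M12. These sum to 12.580%.

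- Mostly early (60/10/10/10/10): 0.6 × 5.000 + 0.1 × (3.774 + 2.532 + 1.274) = 3.76%.
- Even (20 at each visit): 0.2 × 12.580 = 2.52%.
- Mostly late (10/10/10/10/60): 0.1 × (5.000 + 3.774 + 2.532 + 1.274) = 1.26%.

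Timing alone gives a threefold spread, and all three figures lie below the 5% risk. The spread is also about threefold at a 12-month risk of 2% (1.50% vs 0.50%) and of 10% (7.53% vs 2.53%).

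**4. Death.** With a death hazard μ, the expected frequency for T months is λ/(λ+μ) × [1 − exp(−(λ+μ)T)]. With even timing and the 5% risk, it falls from 2.52% with no deaths to 2.42% at 12-month mortality of 10% and 2.21% at 30%. If deaths occur at the first infection itself, 10% and 20% mortality give 2.26% and 2.01%. Death matters, but less than timing.

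**5. Person-time.** Divide expected cases by expected observed time, which for T months is [1 − exp(−(λ+μ)T)]/(λ+μ). The result is λ whatever the timing or mortality: −ln(0.95)/12 × 1,200 = 5.13 per 100 person-years in every scenario of steps 3 and 4 at the 5% risk. This invariance depends on a constant hazard.

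**The case against.** The strongest reply is that the endpoint is secondary and descriptive. The protocol states no test between groups for reinfection, and the share of ever-positive subjects with an observed reinfection is a legitimate crude description. All groups share the same visits and the same 12-month participation, and the protocol gives no timing of first infection by group. A SAP could add rates beside the proportion. All of this stands, and it limits the point to a conditional one. It does not remove it: the objective asks for the frequency during follow-up by group, and such a table will be read across groups whether or not a test is attached.

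A reader might infer more than the document supports in four ways:

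- That the group figures are not comparable at all. They are distorted only if groups differ in timing of first infection or in mortality. With equal mixes and equal mortality the false ratio is 1.00.
- That the problem extends to WP 1. Its objective is "describe the frequency of reinfections in each study population", but WP 1 has its own criterion, a count of reinfections or reactivations with a different case definition. The WP 2 proportion does not govern it.
- That the reported figure must be too low. The shortfall concerns time at risk only. The broad WP 2 case definition could push the number of cases the other way.
- That 0 to 12 months is time since infection. It is observed time after a positive result, inferred from the schedule. A subject infected before inclusion may be further from infection than that, and one first positive at M12 may have been infected up to about three months earlier.

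**Conclusion.** The point holds in conditional form, for the WP 2 criterion only. As defined, the proportion understates the 12-month reinfection risk whenever some first positives fall after M0 or observation is cut short. Group figures will differ spuriously to the extent that groups differ in timing of first infection and, less strongly, in mortality. Under assumed inputs the false ratio runs from 1.00 with equal mixes through 1.30 to 1.96, and reaches about 3 for the most contrasting visit patterns tried. None of the timing mixes, hazards or mortalities comes from the protocol, so these figures show how sensitive the measure is and do not predict its error. The change is worth making because it is cheap, but the primary objective does not depend on it.

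**What to change.** Keep the crude proportion, and beside it report by group the number of reinfections per person-month under observation:

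- **Entry:** the later of M0 and the first in-study positive test, or the end of the first episode where there were symptoms. Starting no earlier than M0 avoids counting months before inclusion, which were not observed and which the subject had to survive in order to enrol. Asymptomatic infections have no episode end, so they enter at the positive test.
- **Exit:** reinfection, death, last contact or M12, whichever comes first.
- **No observation after the first positive:** the subject contributes no time.

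Add the cumulative incidence of reinfection from that entry, with death as a competing event. Give the rates by calendar quarter as well, as WP 4 already does for incidence. Epidemic risk varies over time, and a single crude rate would still depend on when each group was at risk.

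The cost is a revised definition and a little more analysis, with no added visit or sample. The scheduled serology dates a first positive, and duration of the symptomatic phase is already a WP 2 criterion. The synopsis does not say that onset and recovery dates are recorded, so this should be checked against the questionnaires. Silent seroconversions can be dated only to within about three months, and the report should say so.
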